7.2 Cohort 1 - Chronic HBV Anti-Viral Treatment

a. Arm 1: Prophylactic Anti-Viral Therapy

The treating investigator and patient will choose the appropriate anti-viral therapy from one of the three anti-viral therapies below. Patients may initiate anti-viral therapy with a reduced dose based on creatinine clearance (see Dose Modifications, [Section 8.2](#))

Start anti-HBV treatment before anti-cancer therapy or up to 42 days after initial anti-cancer therapy. Continue anti-HBV treatment for 6 months after last dose of anti-cancer therapy or for up to 24 months after registration, whichever occurs first.

Agent	Dose	Route	Start Day	Schedule
Tenofovir alafenamide (TAF)	25 mg ^A	PO ^B	As soon as possible after registration; before or up to 42 days after initial dose of anti-cancer therapy	Daily for up to 6 months after the last dose of anti-cancer therapy or maximum of 24 months ^C
Tenofovir disoproxil fumarate (TDF)	300mg PO		As soon as possible after registration; before the last dose or up to 42 days after initial dose of anti-cancer therapy	Daily for up to 6 months after the last dose of anti-cancer therapy or Maximum of 24 months

Entecavir (ETV)	0.5mg	As soon as possible after registration; before the last dose or up to 42 days after initial dose of anti-cancer therapy or anti-cancer therapy.	Daily for up to 6 months after the last dose of anti-cancer therapy or Maximum of 24 months.
--------------------	-------	---	--

^A In patients taking carbamazepine the TAF dose will be increased to 50 mg daily.

^B See dosage administration details in [Section 3.1d](#).

^C Note: Chronic HBV patients should not abruptly stop antiviral therapy after 24 months. Please see [Section 8.2](#) for details on cessation of anti-HBV therapy in chronic HBV patients.

b. Arm 2: Upon Indication Anti-Viral Therapy

The treating investigator and patient will choose the appropriate anti-viral therapy from one of the three anti-viral therapies below. Patients may initiate anti-viral therapy with a reduced dose based on creatinine clearance (see Dose Modifications, [Section 8.2](#)).

Monitor ALT at least every 4 weeks (+/- 2 weeks) as part of trial monitoring for the first 24 weeks, then every 8 weeks thereafter. If hepatitis flare occurs (see definition for hepatitis flare in [Section 10.2b](#)), then obtain an HBV DNA test per usual care. Start anti-HBV therapy if HBV reactivation occurs.

Agent	Dose	Route	Start Day	Schedule
Tenofovir alafenamide (TAF)	25 mg ^A	PO ^B	As soon as possible after HBV reactivation occurs (see criteria for HBV reactivation Section 10.2a).	Daily for up to 6 months after the last dose of anti-cancer therapy or a maximum of 24 months ^C .
Tenofovir disoproxil fumarate (TDF)	300mg	PO	As soon as possible after HBV reactivation occurs (see criteria for HBV reactivation . Section 10.2a	Daily for up to 6 months after the last dose of anti-cancer therapy or Maximum of 24 months
Entecavir (ETV)	0.5mg	PO	As soon as possible after HBV reactivation occurs (see criteria for HBV reactivation . Section 10.2a	Daily for up to 6 months after the last dose of anti-cancer therapy or Maximum of 24 months.

^A In patients taking carbamazepine the TAF dose will be increased to 50 mg daily.

^B See dosage administration details in [Section 3.1d](#).
^C Note: Chronic HBV patients should not abruptly stop antiviral therapy after 24 months. Please see [Section 8.2](#) for details on cessation of anti-HBV therapy in chronic HBV patients.

Anti-HBV therapy is initiated only when HBV reactivation. Once started, anti-HBV therapy continues for a minimum of 6 months after discontinuation of all anti-cancer therapy or for up to 24 months after registration, whichever comes first.

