7.4 HBV Monitoring and Adverse Liver Outcomes

During anti-cancer therapy and for 24 months from initial registration, all patients will undergo monitoring for HBV reactivation and adverse liver outcomes (see [Section 10.0](#)). Patients will have ALT and total bilirubin assessed every 4 weeks (\pm 2 weeks) for the first 24 weeks, then every 8 weeks thereafter. Per usual care, if total bilirubin > 3 mg/dL or if ALT > 5x IULN or > 200 U/L then INR will be assessed.

As part of adverse liver outcome assessment, if a hepatitis flare occurs (defined as ALT > 3 x baseline and > 100 U/L) the following labs should be ordered on the same day as the flare or within 7 days of the flare:

- direct bilirubin,
- HBV DNA,
- IgM anti-HAV, and
- either anti-HCV or HCV RNA.

- Patients on Arms 1, and 2 must have HBeAg tested. HBV test results must be reported on the **S1614** Laboratory Values Form.
- If Patients on Arms 3 and 4 become HBsAg positive and have a hepatitis flare, HBeAg testing is required. HBV test results must be reported on the **S1614** Laboratory Values Form.

Additionally, for all HBsAg+ patients, it is recommended that the treating investigator contact [name], M.D., [name], M.D., or [name] at [contact] for evaluation during the study treatment and after discontinuation of study treatment to ensure continued monitoring and to determine whether antiviral therapy should be maintained after discontinuation of study treatment.

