7.6 Criteria for Removal from Protocol Treatment

- Completion of 24 months on study.
- If receiving anti-viral treatment, completion of anti-viral treatment 6 months after discontinuing all anti-cancer therapy or for up to 24 months after registration, whichever comes first.
- Cumulative delay of anti-viral treatment > 30 days for any reason.
- Unacceptable toxicity to anti-viral treatment. (See [Section 8.2](#))
- The patient may withdraw from the study at any time for any reason. If the patient allows for indirect follow-up or is refusing to complete any further patient forms but will allow the site to follow them indirectly, continue to submit the site-completed forms through Week 104.

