10.2 Other Endpoints

a. HBV reactivation is defined as one of the following:

- ≥ 2 log (100-fold) increase in HBV DNA compared to baseline in patients with detectable HBV DNA at baseline, or
- HBV DNA ≥ 3 log (1,000) IU/mL in a patient with previously undetectable HBV DNA, or
- HBV DNA ≥ 4 log (10,000) IU/mL if baseline HBV DNA not available, or
- HBsAg seroreversion (HBsAg- to HBsAg+) in a patient previously HBsAg-.

b. Hepatitis flare: Hepatitis flare is defined as ALT $> 3 \times$ baseline and >100 U/L.

c. Upon indication: On Arms 2 and 3, anti-HBV therapy is initiated only when HBV reactivation occurs (see [Section 10.2a](#)). Once started, anti-HBV therapy continues for a minimum of 6 months after discontinuation of all anti-cancer therapy or for up to 24 months after registration, whichever comes first (see [Section 7.6](#)).

d. Cancer therapy interruption is defined as dose reduction, treatment delay, or termination of anti-cancer therapy due to hepatic-related reasons other than disease progression in the liver.

e. Death due to any cause measured from date of randomization to date of death.

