11.2 Secondary Endpoints

The main secondary objective for each randomized cohort is to determine the incidence of HBV reactivation among patients with solid malignancies and chronic or past HBV infection during or after completion of anti-cancer therapy. Based on preliminary data, it is anticipated that 20% of patients will experience HBV reactivation on the standard arm of each of the randomized trials. Estimates of HBV reactivation at one year will be derived using cumulative incidence to account for competing risks. Under this scenario, a sample size of n=222 patients for each randomized study will allow the investigators to estimate the confidence interval to within $\pm 6\%$ (based on the upper bound of the 95% confidence

interval using an exact binomial in patients with complete follow-up), if the assumed incidence is at least 20%. Thus, this sample size will allow the confidence interval to be estimated to within $\pm 31.1\%$ of the assumed incidence (the “relative accuracy”, defined as: (95% CI upper bound – p)/p], where p is the assumed incidence). This estimate is conservative as it is based on the assumption of no information from the 10% of patients estimated to drop out.

The investigators will also compare HBV reactivation rates by arm within each randomized trial. Based on a two-sample survival design accounting for the competing risk of death (~20% deaths at 1 year [hazard rate of 0.223]), and a one-sided alpha=0.05 test, then n=222 patients (111 per arm) will give 81% power to detect a hazard ratio for HBV reactivation for experimental to standard arms of 0.47, representing a 53% reduction in the hazard risk of HBV reactivation in the first year (from a hazard=0.223 down to hazard=0.105), or an absolute reduction of 50% (from 20% down to 10%). Multivariable Cox regression will compare the effect of intervention assignment, adjusting for the stratification factors specified in the main clinical study.

The investigators will also determine the cumulative incidence of the combined endpoint of adverse liver events plus HBV reactivation, as well as the cumulative incidence of hepatitis flare, by arm within each randomized trial and compare it between the arms in similar fashion.

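### Arms 2 and 3 carry conflicting antiviral durations, and the 7.6 completion point can fall before a late reactivator starts treatment

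*Combined protocol and SAP*

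**What the plan says.** **Start.** In Arms 2 and 3 the tables in 7.2 and 7.3 give the start day as "As soon as possible after HBV reactivation occurs". The text of 7.2b and 7.3a likewise says to start if reactivation occurs, with no time limit.

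**Duration.** Three rules are given:
- Tables: the tenofovir alafenamide row for both arms reads "Daily for up to 6 months after the last dose of anti-cancer therapy or a maximum of 24 months", and the other two drugs have the same terms. No origin is given for the 24 months.
- Text under each table, and 10.2c: the antiviral "continues for a minimum of 6 months after discontinuation of all anti-cancer therapy or for up to 24 months after registration, whichever comes first".
- Section 7.6: a patient on an antiviral leaves protocol treatment at "completion of anti-viral treatment 6 months after discontinuing all anti-cancer therapy or for up to 24 months after registration, whichever comes first".

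**Monitoring.** Section 7.4 says that "for 24 months from initial registration, all patients will undergo monitoring for HBV reactivation and adverse liver outcomes". Section 11.2 counts reactivation "during or after completion of anti-cancer therapy".

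**Stopping.** Footnote C under the Arm 1 and Arm 2 tables warns against an abrupt stop after 24 months in chronic HBV and refers to 8.2 for how to stop. Section 8.2 covers toxicity, switching of agents and renal dosing. It warns that withdrawal may provoke a flare but gives no stopping procedure. The relevant guidance is elsewhere: 7.4 recommends contacting study physicians about HBsAg-positive patients, including whether to keep the antiviral going, and the boxed warning in 3.0 calls for close hepatic monitoring and possible resumption.

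**The concern.** A ceiling of 6 months and a floor of 6 months agree at one value only. A floor also sits badly with a clause that ends treatment at the earlier of two dates. These are operative dosing instructions for patients whose virus has reactivated, and different sites could follow different sentences.

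The timing is the more serious matter. The 6-month point in 7.6 is counted from the end of anti-cancer therapy and takes no account of when the antiviral began. In Arms 2 and 3 the start depends on reactivation, which is watched for through month 24. The completion date can therefore come before the start date. A site would then have to treat with no usable statement of how long. Footnote C adds to this by sending sites to a section that does not say how to stop.

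**Working it through.** **1. The wordings side by side**

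| Place | Role of the 6 months | Outer limit |
|---|---|---|
| 7.2 and 7.3 tables, Arms 2 and 3 | ceiling | 24 months, origin not given |
| Text under those tables; 10.2c | floor, then the earlier of two dates | 24 months after registration |
| 7.6 | fixed completion point | 24 months after registration |

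A stop at exactly 6 months meets all three. The Arm 1 text already gives a fixed 6 months, in agreement with 7.6; only the Arm 1 table is looser. Section 10.2c refers the reader on to 7.6.

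**2. Timeline**

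Let D be the months from registration to the end of anti-cancer therapy. The documents do not give D, so it is varied. The 7.6 point is min(D + 6, 24).

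| D | 7.6 point (month) | Months of monitoring left |
|---|---|---|
| 3 | 9 | 15 |
| 6 | 12 | 12 |
| 9 | 15 | 9 |
| 12 | 18 | 6 |
| 18 or more | 24 | 0 |

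Example: anti-cancer therapy ends at month 6 and reactivation occurs at month 13. Treatment must start, but the 7.6 point was month 12. The gap exists only when D is below 18.

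**3. Illustrative size**

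Inputs from 11.1 and 11.2: 111 patients per arm; death hazard 0.223 per year; reactivation hazard "from a hazard=0.223 down to hazard=0.105". These hazards match the plan's one-year rates of 20% and 10%: −ln(0.80) = 0.223 and −ln(0.90) = 0.105. Arm 2 is the standard arm of Cohort 1 (h = 0.223). Arm 3 is the experimental arm of Cohort 2 (h = 0.105).

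Expected reactivations between years a and b, with death competing:

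111 × h/(h + 0.223) × [exp(−(h + 0.223)a) − exp(−(h + 0.223)b)]

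Over 0 to 2 years this gives 32.8 in Arm 2 and 17.1 in Arm 3, about 50 in all.

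For reactivations after the 7.6 point, a = (D + 6)/12 and b = 2. With D = 6, a = 1:
- Arm 2: 111 × 0.500 × (0.6402 − 0.4098) = 12.8
- Arm 3: 111 × 0.3201 × (0.7204 − 0.5189) = 7.2

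Sensitivity: let the hazard drop to h/4 once anti-cancer therapy ends at e = D/12. With g = h/4 + 0.223, the count is

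111 × exp(−(h + 0.223)e) × (h/4)/g × [exp(−g(a − e)) − exp(−g(2 − e))]

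| D | Constant hazard: Arm 2 + Arm 3 | Hazard quartered after therapy |
|---|---|---|
| 3 | 16.98 + 9.35 = 26.3 | 5.08 + 2.55 = 7.6 |
| 6 | 12.78 + 7.16 = 19.9 | 3.76 + 1.93 = 5.7 |
| 12 | 5.68 + 3.29 = 9.0 | 1.61 + 0.87 = 2.5 (2.48, so about 2) |
| 18 or more | 0 | 0 |

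**4. Direction of error**

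Arm 3 treatment begins only after reactivation, so it cannot lower the hazard of a first reactivation. At 0.223, Arm 3 would match Arm 2, and the constant-hazard totals would be 2 × 16.98 = 34.0, 2 × 12.78 = 25.6 and 2 × 5.68 = 11.4. Against that, clinical HBV DNA testing is triggered by hepatitis flare and about 10% of patients are expected to drop out, which lowers every count.

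**The case against.** The best defence is that the intent is clear. Six months satisfies every sentence, the clarifying paragraph sits directly under each table, and 7.6 settles the matter. For patients who reactivate during or soon after anti-cancer therapy, that stands.

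Three stronger readings are tempting and are not supported:
- **A late reactivator may not be treated, or may be treated only by virtue of the floor wording.** Sections 7.2b and 7.3a order a start on reactivation without a time limit. The 7.6 bullet applies to patients already receiving an antiviral, and it governs protocol treatment of commercially available drugs, not medical care. What remains is narrower: once such a patient starts, the completion point is already past and the duration is undefined.
- **The tables license a routine stop before 6 months.** The removal criteria in 7.6 are completion, month 24, cumulative delay, toxicity and withdrawal. A routine earlier stop is not among them, and 8.2 warns against withdrawal.
- **The counts are upper bounds.** They are not, because of the Arm 3 hazard and the assumed constant hazards and end dates.

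It can also be said that footnote C and the stray superscript C in the Arm 3 table are tidying. For the superscript that is right. The 8.2 sentence setting aside exacerbation on discontinuation already confines itself to the period of anti-cancer therapy. The footnote is a modest matter too, since 7.4, 3.0 and the 8-weekly visits off treatment cover much of the risk. But the 7.4 contact is only a recommendation, it covers HBsAg-positive patients only, and the footnote does not lead to it.

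**Conclusion.** The point holds as a conflict in treatment-duration wording with one real failure: no workable duration for Arm 2 or 3 patients who reactivate more than 6 months after anti-cancer therapy ends. It arises only if that therapy ends before month 18.

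The size is uncertain. It is roughly 9 to 26 reactivations under constant planning hazards, and 2 to 8 if the hazard quarters after therapy, for assumed end dates between months 12 and 3. The textual conflict does not depend on these figures. The footnote C pointer is a lesser, separate defect.

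A reader might infer that the primary comparison is compromised. Nothing here shows that, and no effect on power, alpha or bias is claimed. The change is worth making because the instructions concern patients with reactivated virus and the correction is cheap.

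**What to change.** Use one rule in the Arm 2 and 3 tables, the text below them, 10.2c and 7.6: *treat for 6 months beyond the final anti-cancer dose or until month 24 from registration, whichever is earlier; if the antiviral begins more than 6 months after that final dose, treat until month 24 from registration.* Drop the floor wording, since it cannot work alongside an earlier-of-two-dates clause.

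In the Arm 1 table, state a fixed 6 months to match its text.

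Redirect footnote C to the 7.4 evaluation and the 3.0 boxed warning, and apply it to every planned stop in HBsAg-positive patients, not only at month 24. The stray superscript C in the Arm 3 table can be removed at the same time.

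The cost is protocol wording, with somewhat longer antiviral use in a few late reactivators. No visits, tests or patients are added. One limit remains: a patient who reactivates shortly before the 6-month point still gets a short protocol course, so the evaluation at planned stops matters most there.

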7.3 Cohort 2: Past HBV Anti-Viral Treatment

a. Arm 3: Upon Indication Anti-Viral Therapy

The treating investigator and patient will choose the appropriate anti-viral therapy from one of the three anti-viral therapies below. Patients may initiate anti-viral therapy with a reduced dose based on creatinine clearance (see Dose Modifications, [Section 8.2](#)).

Monitor ALT at least every 4 weeks (+/- 2 weeks) as part of trial monitoring for the first 24 weeks, then every 8 weeks thereafter. If hepatitis flare occurs (see definition for hepatitis flare in [Section 10.2b](#)), then obtain HBV DNA test per usual care. Start anti-HBV therapy if HBV reactivation occurs.

Agent	Dose	Route	Start Day	Schedule
Tenofovir alafenamide (TAF)	25 mg ^A	PO ^B	As soon as possible after HBV reactivation occurs (see criteria for HBV reactivation Section 10.2a).	Daily for up to 6 months after the last dose of anti-cancer therapy or a maximum of 24 months ^C .
Tenofovir disoproxil fumarate (TDF)	300mg	PO	As soon as possible after HBV reactivation occurs (see criteria for HBV reactivation. Section 10.2a	Daily for up to 6 months after the last dose of anti-cancer therapy or Maximum of 24 months
Entecavir (ETV)	0.5mg	PO	As soon as possible after HBV reactivation occurs (see criteria for HBV reactivation. Section 10.2a	Daily for up to 6 months after the last dose of anti-cancer therapy or Maximum of 24 months.

^A In patients taking carbamazepine the TAF dose will be increased to 50 mg daily.

^B See dosage administration details in [Section 3.1d](#).

Anti-HBV therapy is initiated only when HBV reactivation. Once started, anti-HBV therapy continues for a minimum of 6 months after discontinuation of all anti-cancer therapy or for up to 24 months after registration, whichever comes first.

b. Arm 4: Usual Care Anti-Viral Therapy

Initiate anti-HBV therapy at the discretion of the physician. Any FDA approved anti-viral medication for treatment of HBV may be utilized. See [Section 18.5](#).

7.4 HBV Monitoring and Adverse Liver Outcomes

During anti-cancer therapy and for 24 months from initial registration, all patients will undergo monitoring for HBV reactivation and adverse liver outcomes (see [Section 10.0](#)). Patients will have ALT and total bilirubin assessed every 4 weeks (\pm 2 weeks) for the first 24 weeks, then every 8 weeks thereafter. Per usual care, if total bilirubin > 3 mg/dL or if ALT > 5x IULN or > 200 U/L then INR will be assessed.

As part of adverse liver outcome assessment, if a hepatitis flare occurs (defined as ALT > 3 x baseline and > 100 U/L) the following labs should be ordered on the same day as the flare or within 7 days of the flare:

- direct bilirubin,
- HBV DNA,
- IgM anti-HAV, and
- either anti-HCV or HCV RNA.

- Patients on Arms 1, and 2 must have HBeAg tested. HBV test results must be reported on the **S1614** Laboratory Values Form.
- If Patients on Arms 3 and 4 become HBsAg positive and have a hepatitis flare, HBeAg testing is required. HBV test results must be reported on the **S1614** Laboratory Values Form.

Additionally, for all HBsAg+ patients, it is recommended that the treating investigator contact [name], M.D., [name], M.D., or [name] at [contact] for evaluation during the study treatment and after discontinuation of study treatment to ensure continued monitoring and to determine whether antiviral therapy should be maintained after discontinuation of study treatment.

